5. STUDY OBJECTIVES

The primary objectives of this pivotal study are:

- To assess the efficacy and safety of S5G4T-1 compared to S5G4T-1 Vehicle when applied once daily for 12 weeks in patients with papulopustular rosacea.

5.1 Secondary Objective

The secondary objective of this pivotal study is:

- To demonstrate statistical superiority in efficacy of S5G4T-1 compared to the vehicle with regard to percent change from baseline.

5.2 Supportive Objective

The supportive objective of this pivotal study is:

- To determine the time required to observe improvement in the efficacy parameters associated with clearance of rosacea for S5G4T-1 compared to vehicle.

5.3 Safety Objective

The safety objectives of this pivotal study are:

- To determine the nature, severity and frequency of the adverse event rate, the Cutaneous Safety Assessment and the Local Tolerability Assessment of S5G4T-1 compared to the vehicle.

6. STUDY DESIGN

6.1 Overall Study Design

This study will be a randomized, double-blind, multicenter, parallel group, active- and vehicle-controlled pivotal study of the efficacy and safety of S5G4T-1 and its vehicle for the treatment of papulopustular rosacea for 12 weeks. Approximately 350 patients with moderate to severe rosacea (rated 3 or 4 on the 5-point IGA scale) will be enrolled at up to 28 sites. Patients in this randomized, double-blind, vehicle-controlled, parallel-group multi-center study will be randomly assigned in a 2:1 ratio to S5G4T-1 or vehicle, respectively. Subjects with severe rosacea who are appropriate for systemic treatment need to be counseled regarding their treatment options by the Principal Investigator.

Patients will receive once daily treatment with S5G4T-1 or vehicle cream for 12 weeks. After the screening period, qualified patients will be randomly assigned at the Baseline visit and treated for 12 weeks. Efficacy assessments will include facial inflammatory lesion counts and IGA assessment ranging from 0 (clear) to 4 (severe). Investigators will be provided with instructions for lesion counts to ensure consistency of procedure. Patient reported outcomes (PRO) will be assessed with the PAPSS (Patient Assessment of Papulopustular Rosacea Signs and Symptoms), PAPI (Patient Assessment of Papulopustular rosacea Impacts), and PGI-S (Patient Global Impression of Symptom Severity) that will be administered at Baseline, Weeks 2, 4, 8, and 12, or at early termination. In addition, the PGI-C (Patient Global Impression of Change), PGI-TS (Patient Global Impression of Treatments Satisfaction), and PGI-SE (Patient Global Impression of Treatments Side Effects) will be administered at Weeks 2, 4, 8, and 12, or at early termination [FDA Guidance 2009]. Safety will be assessed at all visits and will include monitoring local and systemic adverse events (AEs); the Investigator Cutaneous Safety Assessment rating of

erythema, dryness and scaling, and the Local Tolerability Assessments rating of itching and burning/stinging on a scale ranging from 0 (none) to 3 (severe).

Patients will return to centers for IGA, lesion counts, PRO questionnaire, Investigator Cutaneous Safety Assessment, and Local Tolerability Assessments at Weeks 2, 4, 8 and 12. AEs and concomitant medications will be assessed throughout the treatment period. A urine pregnancy test is required at Visit 1, 2, 4, 5, and 6 for all females of child-bearing potential.

Clinical Evaluations will be performed at:

- Visit 1/Screening
- Visit 2/Baseline, Day 1
- Visit 3/Week 2, Day 15 (\pm 3 Days)
- Visit 4/Week 4, Day 29 (\pm 3 Days)
- Visit 5/Week 8, Day 57 (\pm 3 Days)
- Visit 6/Week 12, Day 85 (\pm 4 Days)/End of Treatment)

6.1.1 Schedule of Visits and Assessments

The schedule of assessments can be found in Section 13.9 of the protocol.

6.1.2 Method of Assigning Subjects to Treatment Groups

Patients who satisfy all the inclusion and none of the exclusion criteria will be randomized to one of two treatment arms. Randomization will be performed in the Interactive Web Response System (IWRS) according to a computer-generated randomization schedule. The randomization schedule will be generated by the unblinded statistician and uploaded to the IWRS. The randomization schedule will be maintained securely within the IWRS. Patients will be randomized to E-BPO 5% or vehicle cream, once daily on a 2:1 basis for twelve (12) weeks.

Once a patient is determined eligible for the study at the Baseline visit, the patient will be randomized to study product assignment by the IWRS. Each study product carton will contain four pumps of the same product; The first supplied pump in each kit is marked A (e.g. number of pump within a kit is XXXXA), at Visit 4/ Week 4 the patient will return the pump and will be dispensed with the next pump which is marked B. At Visit 5/ Week 8, the patient will be dispensed with a pump marked C. The pump marked as D is a backup pump. The patient number will be added to both parts of the kit label (open part and tear-off label and to the pump label).

6.1.3 Blinding

The staff involved in data management and statistical evaluation will remain blinded until identification of the analysis population is completed and a database lock memo is issued.

The randomization schedule and treatment code will not be revealed to the patients, study personnel, Sol-Gel or its representatives until after the database lock, except to the Medical Monitor or Principal Investigator for an emergency. Access to the randomization list will be maintained by and limited to the unblinded Biostatistician and the designated personnel directly responsible for labeling of study materials. The Medical Monitor will not have access to the randomization list, but may determine that unblinding one or all patients may be necessary in the case that the safety of study patients is at risk. In an emergency, the study blind may be broken only if:

- In the opinion of the Medical Monitor and/or the Principal Investigator, it is in the patient's best interest to do so
- Knowledge of the treatment will alter the clinical management of the patient

In the case of an emergency that requires unblinding, the Investigator can request to unblind the patient without prior contact with the Medical Monitor although follow-up between the Investigator and Medical Monitor must occur so that all parties are aware of the unblinding. Although it is recommended that the Investigator contact the Medical Monitor prior to unblinding any patient, in instances where this is not feasible or advisable the Principal Investigator may directly access the patient's treatment assignment. In all situations, the IWRS will be used to obtain treatment assignment information with limited access to only the above-designated individuals, and any unblinding will be documented as a protocol deviation.

7. EFFICACY AND SAFETY ENDPOINTS

7.1 Efficacy Endpoints

7.1.1 Primary Efficacy Endpoints

There are two co-primary efficacy endpoints:

- Proportion of patients with the primary measure of success (clear or almost clear) in IGA relative to Baseline at Week 12
- Absolute change in inflammatory lesion counts from Baseline to Week 12

7.1.2 Secondary Efficacy Endpoints

The secondary efficacy endpoints are as follows:

- Percent change in inflammatory lesion count from Baseline to Week 12
- Absolute change in inflammatory lesion count from Baseline to Week 8
- Proportion of patients with the primary measure of success (clear or almost clear) in the IGA relative to Baseline at Week 8
- Absolute change in inflammatory lesion count from Baseline to Week 4
- Proportion of patients with the primary measure of success (clear or almost clear) in the IGA relative to Baseline at Week 4

7.1.3 Additional Supportive Efficacy Endpoints

The supportive efficacy endpoints include the following:

- Percent change in inflammatory lesion count at Week 8
- Percent change in inflammatory lesion count at Week 4
- Mean change comparison in PAPSS item 1 (burning) between groups from Baseline to Weeks 4, 8 and 12
- Mean change comparison in PAPSS item 2 (itching) between groups from Baseline to Weeks 4, 8 and 12
- Mean change comparison in PAPSS item 3 (redness) between groups from Baseline to Weeks 4, 8 and 12
- Mean change comparison in PAPSS item 4 (bumps) between groups from Baseline to Weeks 4, 8 and 12
- Rosacea erythema assessment at Week 12
- Telangiectasia assessment at Week 12
- The proportion of patients in treatment relative to control who report at least “minimally improved” (defined as “very much improved”, “much improved” or “minimally improved”) as measured by the PGI-C at Week 12
- Mean change in the components of the PAPI score between groups from Baseline to Week 12

- Proportion of patients in the treatment relative to control achieving a three-point improvement in the components of the PAPI score from Baseline to Week 12
- PGI-S at Week 12
- PGI-TS at Week 12
- PAPSS within-person absolute change from Baseline to Week 12 (and/or other, earlier time points if so desired)

Other supportive endpoints not outlined in the SAP will be explored by Sol-Gel as appropriate.

7.1.4 Exploratory Endpoints

The exploratory endpoint is the mean change in Rosacea Quality-of-Life (RosaQoL) subscale scores from Baseline to Week 12.

7.2 Safety Endpoints

Safety will be assessed through Cutaneous Safety Assessment, Local Tolerability Assessment, AE reporting, physical examination, vital signs, and PGI-SE.

8. STATISTICAL AND ANALYTICAL PLANS

8.1 General Methodology

All statistical processing will be performed using SAS® version 9.3 or later unless otherwise stated. Statistical significance will be based on two-tailed tests of the null hypothesis resulting in p-values of 0.05 or less. These methods are intended to analyze the results of the study.

The primary method of handling missing efficacy data will be based on estimation using the method of Markov Chain Monte Carlo (MCMC) imputation. This method provides robust estimation when the pattern of missingness is arbitrary. Additionally, the estimation will be done for each treatment group separately so that the pattern of missingness for one group does not influence the estimation of missing data for another group. Groups of complete datasets following the estimation will be concatenated to form analysis datasets for the comparative analyses and subsequent imputation result inference with SAS PROC MIANALYZE.

Descriptive statistics will also be derived from the multiply imputed datasets.

Additionally, a model-based multiple imputation process will be used as a sensitivity analysis to the MCMC imputation. Finally, the absolute change in lesion count will be analyzed using a repeated measures analysis of covariance (ANCOVA) for lesion count data and a repeated measures logistic regression model (generalized estimating equations) for the dichotomized IGA.

8.1.1 Statistical Analysis

All analyses will be performed by QST using SAS® Version 9.3 or later. All summary tables and data listings will be prepared utilizing SAS® software.

The standard operating procedures (SOPs) of QST will be followed in the creation and quality control of all data displays and analyses.

All data listings will be by subject. Additionally, all listings except the screen failure and randomization listings will be by treatment.

8.1.2 Baseline Definition

Baseline is defined as the last non-missing assessment prior to first application of study drug. If the date of first application is unknown due to the subject being lost to follow-up, the Baseline visit record will be used as Baseline if it is non-missing. Missing results will not be flagged as Baseline.

8.1.3 Visit Windowing

Data will be summarized based on nominal visit indications with the exception of data captured at early termination and unscheduled visits. Data from early termination and unscheduled visits will be summarized based on mapped visit values. The analysis windows for early termination and unscheduled visits are presented in the following table.

Analysis Windows for Efficacy and Safety Assessments

Scheduled Visit	Target Study Day	Window (Days)
Week 2	15	8 to 21
Week 4	29	22 to 42
Week 8	57	43 to 70
Week 12	85	71 to 98

Data collected at early termination and unscheduled visits prior to study day 8 will not be analyzed, with the exception of those identified as Baseline values. Data collected at early termination and unscheduled visits after study day 98 will not be included in analyses.

The definition for the study day included in each study window is defined as below:

Study Day prior to Day 1 = Visit Date – Day 1 Date

Study Day on or after Day 1 = Visit Date – Day 1 Date + 1

If an assessment's mapped visit is a visit at which the subject has data from a scheduled visit present, or if no analyses are planned for the assessment at the mapped visit, the data collected at the early termination or unscheduled visit will not be included in analyses.

In the event of multiple values from unscheduled or early termination assessments within an analysis window, the value closest to the scheduled visit target study day will be used for analyses. If two values tie as closest to the time point (for example, one value is before and the other value is after the time point), then the later value will be selected.

Data collected at all visits will be included in the data listings with visit presented as reported by the site.

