Patients will return to centers for IGA, lesion counts, PRO questionnaire, , Investigator Cutaneous Safety Assessment and Local Tolerability Assessments at Weeks 2, 4, 8 and 12. At Week 12 (or at the early termination visit) patients will be asked to complete RosaQoL questionnaire. Adverse events and concomitant medications will be assessed throughout the treatment period. A urine pregnancy test is required at Visit 1, 2, 4, 5 and 6 for all females of child-bearing potential.

Clinical Evaluations will be performed at:

- Visit 1/Screening
- Visit 2/Baseline, Day 1
- Visit 3/Week 2, Day 15 (\pm 3 Days)
- Visit 4/Week 4, Day 29 (\pm 3 Days)
- Visit 5/Week 8, Day 57 (\pm 3 Days)
- Visit 6/Week 12, Day 85 (\pm 4 Days)/End of Treatment)

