13.9. Study Flow Chart

Procedures	Visit 1 ¹	Visit 2 ²	Visit 3 ²	Visit 4 ²	Visit 5 ²	Visit 6 ^{2,3} (EOT ⁴ / EOS ⁵)
Name of Visit	Screening -35 – 0	Baseline Day 1	Week 2 Day 15	Week 4 Day 29	Week 8 Day 57	Week 12 Day 85
Visit window			± 3 days	± 3 days	± 3 days	± 4 days
Informed Consent	X					
Demographics	X					
Medical History/Previous Therapies	X	X				
Brief Physical Examination		X				X
Inclusion/Exclusion Criteria	X	X				
Urine Pregnancy Test ⁶	X	X		X	X	X
IGA	X	X	X	X	X	X
Inflammatory Lesion Counts	X	X	X	X	X	X
Assessment of Eligibility		X				
Rosacea Erythema Assessment		X	X	X	X	X
Telangiectasia Assessment		X	X	X	X	X
Randomization		X				
Cutaneous Safety Assessment and Local Tolerability Assessments		X	X	X	X	X
Administer/ Review Patient Instructions		X	X	X	X	
Weigh Study Product		X		X	X	X
Study Product Dispensed		X ⁷		X	X	
Provide Cleanser and Moisturizer/Sunscreen ⁸		X				
Diary Card dispensed		X		X	X	
Study Product Collected				X	X	X
Diary Card collected				X	X	X
Patient Compliance Reviewed (Diary)			X	X	X	X
Concomitant Therapy and Medication History Reviewed	X	X	X	X	X	X
Adverse Events	X ⁹	X	X	X	X	X
Photography (select site(s))		X	X	X	X	X
Complete PAPSS, PAPI and PGI-S ^{10,11}		X	X	X	X	X
Complete PGI-C, PGI-TS and PGI-SE ¹²			X	X	X	X
Complete RosaQoL ¹³		X				X

¹ If no washout is needed, Visits 1 and 2 may occur on the same day. If a washout is needed, Visit 2 must occur within 35 days of Visit 1.

² All visit dates are in reference to Baseline, e.g., Visit 5 occurs 8 weeks ± 3 days after Baseline Visit.

³ All Week 12 procedures should be completed for Patients who terminate early.

⁴ EOT – end of treatment

⁵ EOS – end of study

⁶ All women of childbearing potential

⁷ Dispense one pump of test material at the Baseline Visit and dispense additional pump at Visit 4 and 5.

⁸ Or study approved cleanser and moisturizer

⁹ Adverse events after ICF is signed will be collected.

¹⁰ PAPSS is Patient Assessment of Papulopustular rosacea Signs and Symptoms; PAPI is Patient Assessment of Papulopustular rosacea Impacts; PGI-S is Patient Global Impression of Symptom Severity. Questionnaires will be completed prior to PI assessment.

¹¹ In case Screening Visit and Baseline are at the same day, the PRO questionnaires should be completed prior to screening procedures.

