19.6.1. Vital Sign Measurements

Vital signs as well as changes from Baseline in vital sign measurements will be summarized with descriptive statistics for each treatment group at all applicable study visits.

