	Not Related	xx (xx.x%)	xx (xx.x%)
xxxxxxxxxxxxxxxxxxxxxxxxxxxxxxxx	Related	xx (xx.x%)	xx (xx.x%)
	Not Related	xx (xx.x%)	xx (xx.x%)

^a Counts reflect numbers of subjects reporting one or more serious adverse events that map to MedDRA. At each level of summarization (System Organ Class or Preferred Term) subjects are counted once under the greatest reported relationship.

Note: MedDRA Version 21.0.

Treatment-emergent adverse events are those events that were not indicated as occurring prior to first application.

Related defined as “Definitely”, “Probably”, or “Possible”. Not Related defined as “Unlikely” or “Not related”.

SOURCE: USERNAME\SPONSOR\PROJECT\JOBNAME (DATE, TIME)

Table 14.3.1.4.1: Summary of Vital Signs
(Safety Population)
(Page 1 of 5)

Temperature (°C)	E-BPO 5% Cream (N=xxx)	Vehicle Cream (N=xxx)
Baseline		
n	xxx	xxx
Mean	xx.x	xx.x
SD	xx.xx	xx.xx
Median	xx.x	xx.x
Min. to Max.	xx to xx	xx to xx
Week 12		
n	xxx	xxx
Mean	xx.x	xx.x
SD	xx.xx	xx.xx
Median	xx.x	xx.x
Min. to Max.	xx to xx	xx to xx
Change from Baseline		
n	xxx	xxx
Mean	xx.x	xx.x
SD	xx.xx	xx.xx
Median	xx.x	xx.x
Min. to Max.	xx to xx	xx to xx

Note: No imputation of missing values. Negative change values represent decrease from Baseline.

SOURCE: USERNAME\SPONSOR\PROJECT\JOBNAME (DATE, TIME)

Table 14.3.1.4.1: Summary of Vital Signs
(Safety Population)
(Page 2 of 5)

Respiratory Rate (breaths/min)	E-BPO 5% Cream (N=xxx)	Vehicle Cream (N=xxx)
Baseline		
n	xxx	xxx
Mean	xx.x	xx.x
SD	xx.xx	xx.xx
Median	xx.x	xx.x
Min. to Max.	xx to xx	xx to xx
Week 12		
n	xxx	xxx
Mean	xx.x	xx.x
SD	xx.xx	xx.xx
Median	xx.x	xx.x
Min. to Max.	xx to xx	xx to xx
Change from Baseline		
n	xxx	xxx
Mean	xx.x	xx.x
SD	xx.xx	xx.xx
Median	xx.x	xx.x
Min. to Max.	xx to xx	xx to xx

Note: No imputation of missing values. Negative change values represent decrease from Baseline.

SOURCE: USERNAME\SPONSOR\PROJECT\JOBNAME (DATE, TIME)

Table 14.3.1.4.1: Summary of Vital Signs
(Safety Population)
(Page 3 of 5)

Systolic Blood Pressure (mmHg)	E-BPO 5% Cream (N=xxx)	Vehicle Cream (N=xxx)
Baseline		
n	xxx	xxx
Mean	xx.x	xx.x
SD	xx.xx	xx.xx
Median	xx.x	xx.x
Min. to Max.	xx to xx	xx to xx
Week 12		
n	xxx	xxx
Mean	xx.x	xx.x
SD	xx.xx	xx.xx
Median	xx.x	xx.x
Min. to Max.	xx to xx	xx to xx
Change from Baseline		
n	xxx	xxx
Mean	xx.x	xx.x
SD	xx.xx	xx.xx
Median	xx.x	xx.x
Min. to Max.	xx to xx	xx to xx

Note: No imputation of missing values. Negative change values represent decrease from Baseline.

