60-100 mmHg	xx (xx.x%)	xx (xx.x%)	xx (xx.x%)	xx (xx.x%)	xx (xx.x%)	xx (xx.x%)
>100 mmHg	xx (xx.x%)	xx (xx.x%)	xx (xx.x%)	xx (xx.x%)	xx (xx.x%)	xx (xx.x%)

Note: No imputation of missing values.

SOURCE: USERNAME\SPONSOR\PROJECT\JOBNAME (DATE, TIME)

Table 14.3.1.5: Summary of Abnormal Physical Examination Findings by Visit
(Safety Population)

	E-BPO 5% Cream (N=xxx)	Vehicle Cream (N=xxx)
Heart		
Baseline		
n	xx	xx
Abnormal	xx (xx.x%)	xx (xx.x%)
Week 12		
n	xx	xx
Abnormal	xx (xx.x%)	xx (xx.x%)
Lung		
Baseline		
n	xx	xx
Abnormal	xx (xx.x%)	xx (xx.x%)
Week 12		
n	xx	xx
Abnormal	xx (xx.x%)	xx (xx.x%)
Abdomen		
Baseline		
n	xx	xx
Abnormal	xx (xx.x%)	xx (xx.x%)
Week 12		
n	xx	xx
Abnormal	xx (xx.x%)	xx (xx.x%)

Note: No imputation of missing values.

SOURCE: USERNAME\SPONSOR\PROJECT\JOBNAME (DATE, TIME)

Table 14.3.1.6: Summary of Patient Global Impression of Treatment Side-Effects (PGI-SE) at Each Evaluation
(Safety Population)
(Page 1 of 2)

Right now, how bothered are you by the side effects of your rosacea treatment:	E-BPO 5% Cream (N=xxx)	Vehicle Cream (N=xxx)
Week 2		
n	xx	xx
0 - I am not bothered	xx (xx.x%)	xx (xx.x%)
1 - I am somewhat bothered	xx (xx.x%)	xx (xx.x%)
2 - I am moderately bothered	xx (xx.x%)	xx (xx.x%)
3 - I am very bothered	xx (xx.x%)	xx (xx.x%)
4 - I am extremely bothered	xx (xx.x%)	xx (xx.x%)
Week 4		
n	xx	xx
0 - I am not bothered	xx (xx.x%)	xx (xx.x%)
1 - I am somewhat bothered	xx (xx.x%)	xx (xx.x%)
2 - I am moderately bothered	xx (xx.x%)	xx (xx.x%)
3 - I am very bothered	xx (xx.x%)	xx (xx.x%)
4 - I am extremely bothered	xx (xx.x%)	xx (xx.x%)

Note: No imputation of missing values.

SOURCE: USERNAME\SPONSOR\PROJECT\JOBNAME (DATE,TIME)

Table 14.3.1.6: Summary of Patient Global Impression of Treatment Side-Effects (PGI-SE) at Each Evaluation
(Safety Population)
(Page 2 of 2)

Right now, how bothered are you by the side effects of your rosacea treatment:	E-BPO 5% Cream (N=xxx)	Vehicle Cream (N=xxx)
Week 8		
n	xx	xx
0 - I am not bothered	xx (xx.x%)	xx (xx.x%)
1 - I am somewhat bothered	xx (xx.x%)	xx (xx.x%)
2 - I am moderately bothered	xx (xx.x%)	xx (xx.x%)
3 - I am very bothered	xx (xx.x%)	xx (xx.x%)
4 - I am extremely bothered	xx (xx.x%)	xx (xx.x%)
Week 12		
n	xx	xx
0 - I am not bothered	xx (xx.x%)	xx (xx.x%)
1 - I am somewhat bothered	xx (xx.x%)	xx (xx.x%)
2 - I am moderately bothered	xx (xx.x%)	xx (xx.x%)
3 - I am very bothered	xx (xx.x%)	xx (xx.x%)
4 - I am extremely bothered	xx (xx.x%)	xx (xx.x%)

[figure not shown]

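### Early-termination vital signs and physical-examination results before Day 71 are collected but left out of the SAP's only post-baseline tables for them

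*SAP*

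**What the plan says.** **Collection.** Protocol 13.7 makes vital signs part of the brief physical examination. The flow chart (Protocol 13.9) schedules that examination at Baseline and Visit 6 only, and Protocol 13.14 treats Visit 6 as Week 12, end of treatment or early termination. Footnote 3 of the flow chart reads "All Week 12 procedures should be completed for Patients who terminate early".

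**Assignment to visits.** SAP 8.1.3 uses nominal visits for scheduled data but not for ET or unscheduled data: "Data from early termination and unscheduled visits will be summarized based on mapped visit values". The windows are Days 8 to 21 (Week 2), 22 to 42 (Week 4), 43 to 70 (Week 8) and 71 to 98 (Week 12). The window table is headed as covering efficacy and safety assessments. ET data before Day 8 are not analysed unless they serve as Baseline. A further clause says that "if no analyses are planned for the assessment at the mapped visit, the data collected at the early termination or unscheduled visit" are dropped from the analyses. All visits still appear in the listings.

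**Tabulation.** In the SAP shells, "Table 14.3.1.4.1: Summary of Vital Signs" (14.3.1.4.1) has Baseline, Week 12 and change on every page. The shift table (14.3.1.4.2) is Baseline by Week 12. "Table 14.3.1.5: Summary of Abnormal Physical Examination Findings by Visit" has Baseline and Week 12. Protocol 19.6.1 says vital signs and their changes are to be "summarized with descriptive statistics for each treatment group at all applicable study visits".

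**The concern.** The protocol asks for a vital-sign and physical-examination assessment when a patient leaves early, and SAP 7.2 names both among the safety assessments. For these two assessments there is only one post-baseline column to land in, Week 12. The mapping rule sends most possible ET days to Week 2, 4 or 8, where that column does not exist, and the no-planned-analysis clause then removes the value. No imputation restores it, because SAP 8.1.5 summarises safety data other than medication dates as observed.

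Patients who stop before Day 71, including those who stop for an adverse event, therefore add nothing post-baseline to the vital-sign change table, the vital-sign shift table or the abnormal-findings table. SAP 8.8.4.3 introduces the shift categories in order to pick out potentially important values, so leaving out the exit measurement of patients who stopped works against its stated use.

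The outcome looks unintended. Dryness, scaling, itching, burning/stinging and PGI-SE are tabulated at Weeks 2, 4, 8 and 12, so the same mapping can keep their ET values from Day 8. Table 14.0.2.1 also uses a combined Week 12/ET label. If the data carry that as one visit name, a programmer could put ET results in the Week 12 rows despite SAP 8.1.3.

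**Working it through.** **1. Reproduce the windows.** Target days are 1, 15, 29, 57 and 85. The midpoints give the lower bounds: (1+15)/2 = 8, (15+29)/2 = 22, (29+57)/2 = 43, (57+85)/2 = 71. The last upper bound is 85 + 14 − 1 = 98. All agree with SAP 8.1.3.

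**2. Pass each possible ET day through the rule** for an assessment tabulated only at Baseline and Week 12.

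| ET study day | Days | Assigned to | Planned row? | Result |
|---|---|---|---|---|
| 2–7 | 6 | none (Day 8 sentence) | – | listing only |
| 8–21 | 14 | Week 2 | no | listing only |
| 22–42 | 21 | Week 4 | no | listing only |
| 43–70 | 28 | Week 8 | no | listing only |
| 71–84 | 14 | Week 12 | yes | tabulated |

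Days 2 to 7 are lost through the Day 8 sentence, and Days 8 to 70 through the no-planned-analysis clause. Excluded days: 6 + 14 + 21 + 28 = 69, out of 69 + 14 = 83.

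**3. Turn days into a share of ET visits.** The documents give neither a dropout rate nor its timing, so timing is an assumption. Day 80 is the last day before the protocol's Week 12 window opens (85 − 4 = 81).

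| Assumed ET timing | Excluded / possible days | Share |
|---|---|---|
| Uniform, Days 2–84 | 69/83 | 83.1% |
| Uniform, Days 2–80 | 69/79 | 87.3% |
| Uniform, Days 29–80 | 42/52 | 80.8% |
| Uniform, Days 57–80 | 14/24 | 58.3% |

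Under a constant hazard with a fraction d gone by Day 84, h = −ln(1 − d)/84, and the share before Day 71 is (1 − e^(−70h))/(1 − e^(−84h)). For d = 10%, h = 0.10536/84 = 0.001254 and the share is 0.0841/0.10 = 84.1%. For d = 5% it is 83.7%, and for d = 30% it is 85.7%.

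All these shares are of patients who attend an ET visit. A patient lost to follow-up has no value for the rule to remove.

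**The case against.** The strongest reply is that this is a choice of display, stated in advance, with little consequence. Every value is listed (Listings 16.2.8.2 and 16.2.8.3). Harm in patients who stop early is reported elsewhere. Adverse events are summarised without visit windows, Table 14.3.1.2.1 has rows for stopping drug or study because of an event, and Listing 16.2.7.2.5 covers those patients. An unfavourable sign found at ET meets the definition in Protocol 17.2 and is reportable under 17.4. All of this stands. A reader might infer that safety signals are being hidden, and the documents do not support that.

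A second reply is that Protocol 19.6.1 is not breached, because Weeks 2, 4 and 8 are not visits at which vital signs apply. That is a fair reading, so the point does not rest on a contradiction with that section. It rests on the protocol requiring the ET measurement and the SAP giving it no place in any table.

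A third reply concerns RosaQoL, which is also tabulated only at Baseline and Week 12, while Protocol 11 says "At Week 12 (or at the early termination visit) patients will be asked to complete RosaQoL questionnaire". It is tempting to extend the criticism to it. However, Protocol 19.4.5 and SAP 7.1.4 define that exploratory endpoint as change from Baseline to Week 12. A score from, say, Day 20 is not a Week 12 score, so leaving it out agrees with the definition. The reply holds for RosaQoL. It does not answer the point for vital signs and physical examination.

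**Conclusion.** The mechanism follows directly from SAP 8.1.3 and the three table shells: ET vital-sign and physical-examination results before Day 71 appear only in listings. The consequence is limited to descriptive safety tables.

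Two wider readings go too far. First, early discontinuers as a whole are not excluded, since an ET visit from Day 71 to Day 98 maps to Week 12 and is kept. Second, a count of affected patients cannot be taken from the documents. For example, 10% of 351 is 35.1, and 35.1 × 0.831 = 29.2. That figure needs an assumed dropout rate, an assumed timing and every discontinuer attending ET. Protocol 13.2 asks only for every effort, and it lists loss to follow-up and withdrawn consent among the reasons for leaving.

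What can be said is the share under stated timing: 83% if uniform over Days 2 to 84, and about 58% if all ET visits fall on Days 57 to 80. That most attended ET visits are affected is an inference from assumed timing; it would fail if discontinuation clustered after Day 70. This is a modest gap that is cheap to close.

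**What to change.** Add one sentence to SAP 8.1.3: for assessments scheduled after baseline only at Week 12/ET (vital signs and physical examination), the ET value is also summarised whatever its study day. Present it in a separate row or panel labelled *Last post-baseline value (Week 12 or ET)* in Tables 14.3.1.4.1, 14.3.1.4.2 and 14.3.1.5, and keep the Week 12 rows as they are. The same sentence tells programmers how to treat a combined Week 12/ET visit label.

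Leave the RosaQoL Week 12 endpoint unchanged; a separate last-value row there is optional.

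The cost is one SAP sentence and an added row or panel in three shells, with no new data. SAP Section 2 allows updates until the blind is broken. The small downside is that the added row mixes treatment durations, which its label makes plain.
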